
Overall objective:	To compare two approaches for the timing of ART initiation in PLHIV with presumptive TB but no signs of CNS disease ("ART first" versus "TB results first") with regard to HIV viral suppression, engagement in care, serious adverse events (SAEs) and adverse events (AEs) consistent with TB-IRIS (AEs of special interest, AESIs) in a pragmatic randomized trial reflecting routine primary and secondary care setting in southern Africa.
Hypothesis	For PLHIV with presumptive TB, but no signs of CNS disease, same day ART ("ART first") is non-inferior to rapid ART ("TB results first") for being retained in care with suppressed HIV viral load (VL) 26 weeks after enrolment.
Endpoints:	
Primary endpoint
 
 
- HIV viral suppression (VL <400 copies/mL) 26 (range 22 – 40) weeks after enrolment
 
 
Secondary and safety endpoints
 
 
- Retention in care 26 (22 – 30) weeks after enrolment
 
- Engagement in care 26 (22 – 30) weeks after enrolment
 
- Disengagement from care 26 (22 – 30) weeks after enrolment
 
- Lost to follow-up 26 (22 – 30) weeks after enrolment
 
- Non-traumatic mortality, SAEs, and AESIs (see section 7.1 for definition) during the first 30 weeks after enrolment
 
- Incidence of TB disease (microbiologically confirmed and/or clinical diagnosis) during the first 30 weeks after enrolment
 
- HIV viral suppression at 26 (22 – 40) weeks using different thresholds (<20 copies/mL; <100 copies/mL; <1000 copies/mL)
 
- ART initiation within 7 and within 28 days after enrolment
 

Study design:	Prospective, parallel, open-label, 1:1 individually randomized, non-inferiority trial

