## 9 STATISTICS

### 9.1 Sample size

The sample size has been calculated with regard to the primary endpoint of the study. Secondary endpoints have not been considered for the determination of the sample size. The expected proportion with viral suppression at 26 weeks after enrolment in the “TB results first” arm is expected to be 75%. To test the hypothesis of non-inferiority of the primary outcome between the two arms, we set the non-inferiority margin to 10%, the power to 80%, and a one-sided alpha level of 0.025. These assumptions yield a sample size of 295 participants per arm.

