### 9.2 Analysis

All analyses will be done by the trial statistician using R (the R Foundation for Statistical Computing) or Stata (version 14, Stata Corporation, Austin/Texas, USA). Analysis will follow CONSORT guidelines. A flowchart will describe the inclusion and follow-up of participants by study arm. Baseline characteristics will be described by study arm with summary statistics such as median and interquartile range or number and percentage; no formal testing between arms will be performed. Outcomes will be described by arm using summary statistics. A detailed statistical analysis plan will be developed separately.

The following analysis sets will be used in this trial:

1. Modified Intention-to-treat (mITT): anyone found to be ineligible after randomization (i.e., pregnant, had not been off ART for  $\geq 90$  days, etc.) will be excluded.
2. Per-protocol (PP) set: This set includes all participants who completed the study without a major protocol deviation (definitions in Statistical Analysis Plan).
3. Complete-case set: all individuals for which the endpoint data could be ascertained.

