#### 9.2.1 Primary analysis

The primary analysis for this study will be the comparison of viral suppression rates between the two study arms. Individuals who do not have documented VL 22 – 40 weeks after enrolment, died, transferred out without a documented VL, or were lost to follow-up will be considered to have a negative outcome (i.e., not achieved viral suppression). The analysis will use a logistic regression model adjusted for the pre-specified randomization stratification factors. Moreover, we will adjust for the most important baseline characteristics if found to be unbalanced (gender, age, ART naive vs reinitiating ART, number and type of TB symptoms) between study arms. For the non-inferiority comparison between the two arms, a CI approach will be used. A figure illustrating the confidence intervals for the risk differences and the non-inferiority margin will be presented. If the lower bound of the confidence interval for the risk difference does not include the non-inferiority margin, then the intervention will be considered non-inferior. Primary analyses for the non-inferiority comparison will be performed on the mITT, per-protocol, and complete case sets. If the “ART first” arm is found to be non-inferior to the “TB results first” arm in the mITT and per-protocol sets, then we will assess for superiority using the mITT set. Further details will be provided in the statistical analysis plan.

As a sensitivity analysis for the primary analysis, primary endpoint information obtained from the tracing visit will not be included.

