Death due to non-trauma	“While alive” approach	Those with the IE prior to VL measurement are included as failures; those with the IE after their VL measurement are included with their endpoint.
Death due to trauma	“While alive” approach	If the endpoint is measured prior to the IE, will be included.
Death due to trauma	“Principal stratum” approach	If the endpoint is not measured prior to the IE, these individuals will be excluded assuming the IE is independent of treatment allocation.

Lost to follow-up	“Composite” approach	No viral load measured. Those with the IE would be considered to have failed treatment and are therefore included as part of the endpoint definition above.
-------------------	----------------------	---

[1] Intercurrent events are post-randomization events that affect either the interpretation or existence of the outcome data associated with the clinical question of interest. . [2] Intercurrent events are post-randomization events that affect either the interpretation or existence of the outcome data associated with the clinical question of interest. [3] The case where individuals had blood drawn for a viral load test, but the test was invalid or failed will be handle with imputation if numbers allow.

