### Primary outcome analysis

The primary analysis for this study will be the comparison of viral suppression rates between the two study arms. For the primary outcome, we will summarize the numbers and percentages of participants included in the analysis, and experiencing the intercurrent events, as per Tables 2a and 2b.

The analysis will use a modified Poisson regression with a log link and robust standard errors to calculate risk differences (10,11). The model will be adjusted for country, the pre-specified randomization stratification factor. (12) Moreover, we will adjust for the most important baseline characteristics (age, gender, CD4 cell count, and ART status) if found to be unbalanced between study arms. In the case of convergence issues, we will use marginal standardization to obtain the risk differences (13).

For the non-inferiority comparison between the two arms, a CI approach will be used. A figure illustrating the confidence intervals for the risk differences and the non-inferiority margin will be presented. If the lower bound of the confidence interval for the risk difference does not include the non-inferiority margin, then the intervention will be considered non-inferior.

For the non-inferiority comparison in the per-protocol analysis, we will use weighting techniques to re-weight the population (14) to account for a potential lack of exchangeability introduced by excluding individuals where the offer of ART did not follow the intervention strategy.

In addition to the absolute effect measure of risk differences, we will report the relative effect of the intervention as well with odds ratios and risk ratios as recommended by the CONSORTs statement (6).

As per section 3.4, if the intervention is found to be non-inferior to the control arm in both the ITT and per-protocol population, then we will assess for superiority under the superiority comparison approach (Table 2a) by assessing whether the 95% CI for the risk difference excludes 0.

We will conduct a complete case analysis in which only individuals with a valid VL measurement in the endpoint window of 22 to 30 weeks is included.

We will summarize what proportion of the primary outcome information came from tracing activities.

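### The complete-case analysis in SAP 6.2 drops known non-trauma deaths before a viral load, so this supplementary comparison is conditional on surviving to a viral load

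*SAP*

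**What the plan says.** SAP 6.2 (Primary outcome analysis) plans one complete-case comparison: "We will conduct a complete case analysis in which only individuals with a valid VL measurement". The rest of the sentence places that VL in weeks 22 to 30. Elsewhere SAP 6.1 and Table 1 set the primary outcome window at days 154-280, that is weeks 22 to 40.

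On non-trauma death, SAP Tables 2a and 2b carry the same rule: "Those with the IE prior to VL measurement are included as failures". A death after the VL leaves the VL result in place. Both tables also write the absence of non-trauma death into the endpoint itself. Protocol 9.2.1 lists death among the events that count as a negative outcome.

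Protocol 9.2 defines the set differently from the SAP: "Complete-case set: all individuals for which the endpoint data could be ascertained". It states no requirement for a VL.

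The documents also differ on the status of this analysis. Protocol 9.2.1 says: "Primary analyses for the non-inferiority comparison will be performed on the mITT, per-protocol, and complete case sets". SAP 4.3 puts the primary non-inferiority analyses on ITT and per-protocol only. The protocol synopsis declares non-inferiority on per-protocol and mITT. In protocol 9.2.1 and SAP 3.4 the step to superiority depends on (m)ITT and per-protocol.

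**The concern.** The usual value of a complete-case result beside a missing-equals-failure analysis is that it varies one thing: how unknown outcomes are treated. Here it varies two. Someone known to have died of a non-trauma cause before a VL has a determined endpoint, namely failure. Requiring a VL removes that person along with those whose status is unknown.

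The exclusion follows an event after randomization that is part of the endpoint, and the protocol gives reason to think it could differ by arm. Section 11.2 expects more IRIS with earlier ART, and more attrition and AIDS-related complications with deferral. Section 2.3 links delay to pre-treatment mortality. If deaths were unequal, the complete-case estimate would leave that part of the effect out, in either direction. A reader comparing it with the ITT result could not tell whether a gap came from missing data or from deaths.

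The VL window is a separate matter. Extending it to week 40 would still leave out every death before a VL.

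**Working it through.** **The plan's own figure.** Protocol 9.1 states: "we set the non-inferiority margin to 10%, the power to 80%, and a one-sided alpha level of 0.025". With 75% suppression in both arms (synopsis) and 1:1 allocation, n per arm = 2 × 0.75 × 0.25 × (1.960 + 0.842)² / 0.10² = 294.33, rounded up to 295. This agrees with "These assumptions yield a sample size of 295 participants per arm". Power at 295 per arm is 80.1%. Nothing below changes the sample size.

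**Assumptions.** The documents give no mortality rate and no missing-VL rate, so these are assumed:
- m, without a VL for reasons other than death: 5%, 10% or 15%, the same in both arms
- d_C, non-trauma death before VL in the 'TB results first' arm: 2%
- d_A, the same in the 'ART first' arm: 3% to 5%
- s, suppression among those with a VL: equal in both arms and set so that the control composite is 75%
- no trauma deaths; 295 per arm; expected counts; Wald 95% intervals

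**Formulas.**
- s = 0.75 / (1 − m − d_C)
- ITT-type composite: RD = s(1 − m − d_A) − 0.75
- Complete case as written (VL required): RD = s − s = 0
- Complete case with deaths kept as failures: RD = [s(1 − m − d_A) − 0.75] / (1 − m) = −s(d_A − d_C) / (1 − m)

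**One case in full** (m = 10%, d_C = 2%, d_A = 5%). s = 0.75/0.88 = 0.852. Composite RD = 0.852 × 0.85 − 0.75 = −2.6 points. With deaths kept, RD = −0.852 × 0.03/0.90 = −2.8 points. As written, RD = 0.0.

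**Results** (risk difference in points, 95% lower bound in brackets):

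| m | d_C v d_A | ITT-type composite | Complete case as written | Complete case, deaths kept |
|---|---|---|---|---|
| 5% | 2% v 3% | −0.8 (−7.8) | 0.0 (−6.6) | −0.9 (−7.6) |
| 5% | 2% v 5% | −2.4 (−9.5) | 0.0 (−6.7) | −2.6 (−9.4) |
| 10% | 2% v 3% | −0.9 (−7.9) | 0.0 (−6.1) | −0.9 (−7.4) |
| 10% | 2% v 5% | −2.6 (−9.7) | 0.0 (−6.2) | −2.8 (−9.4) |
| 15% | 2% v 3% | −0.9 (−7.9) | 0.0 (−5.2) | −1.1 (−6.8) |
| 15% | 2% v 5% | −2.7 (−9.8) | 0.0 (−5.3) | −3.2 (−9.1) |

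Results for d_A = 4% lie between the two rows for each m. With equal mortality every difference is 0.0.

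As written, the estimate stays at 0.0 whatever the mortality gap. With deaths kept it moves by roughly 0.9 to 1.1 points for each point of excess mortality. No lower bound in the table reaches −10.

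**Outside this range.** At an assumed 3% v 8% with m = 10%, the composite is −4.3 (lower bound −11.5), the complete case as written 0.0 (−6.1), and the complete case with deaths kept −4.8 (−11.5). The two forms of complete case now disagree about the margin, but the composite has already failed it.

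**The case against.** The strongest answer is that this analysis decides nothing. Non-inferiority and the step to superiority rest on (m)ITT and per-protocol, and both count these deaths as failures. That stands, and it limits the point to a supplementary result. Protocol 9.2.1 does list complete case as primary, but the synopsis and the SAP do not use it for the decision.

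A reader might infer that the trial would hide a mortality difference. The documents do not support that. Non-traumatic mortality is a secondary endpoint and is summarized (SAP 6.2), safety outcomes are reported by arm (SAP 6.5), and intercurrent events, death included, are tabulated (SAP 6.2). Only the complete-case estimate fails to reflect it.

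A reader might also infer that the VL-only set could produce a false finding of non-inferiority. One can build a case in which the two forms of complete case disagree: 15% otherwise missing, deaths 2% v 5%, and suppression among those measured 90.4% v 88%. As written this gives −2.4 (95% CI −7.9 to 3.2), and with deaths kept −5.4 (−11.6 to 0.7). But it needs an added 2.4-point deficit in suppression, and the ITT-type composite on the same inputs is −4.6 (−11.8 to 2.6). Non-inferiority has already failed there, and complete case could not rescue it.

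It can be said that loss to follow-up is also a failure in Tables 2a and 2b, so death is no more known than loss. This is only partly right. A person lost to follow-up is assigned failure and might in fact be suppressed; for someone dead before a VL there is no other value to find.

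The conflict with the protocol is also arguable. Section 4.1.1 describes the endpoint by its VL sources, which allows a VL-only reading of the complete-case set, while section 4.2.2 speaks of ascertaining death. The protocol wording favours including known deaths without settling it.

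Finally, a VL-only analysis is a conventional supplement, and the SAP does not state what its complete-case analysis is for. That supports keeping such a result if it is labelled for what it is.

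**Conclusion.** The point holds in limited form. As written, the complete-case analysis removes participants whose outcome the estimand already fixes as failure. It therefore compares suppression among those who lived to a VL in weeks 22-30; deaths after that VL stay in.

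Under the assumed rates the estimate is 0.0 where keeping deaths gives about −0.9 to −3.2 points, roughly 9% to 32% of the 10-point margin. None of those scenarios changes the non-inferiority reading. The SAP expects these events to be rare, and at a 1-point excess the effect is about 1 point. All sizes depend on assumed mortality, assumed missingness and equal suppression among those measured.

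The ITT and per-protocol decision and the mortality reporting are unaffected. This is an inexpensive improvement to how a supporting analysis can be read, not a threat to the main conclusion.

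**What to change.** In SAP 6.2, define the complete-case set as participants with a valid VL in the primary window, plus participants known to have died of a non-trauma cause before a VL, scored as failures as in Tables 2a and 2b. Exclude only those whose endpoint is unknown; trauma deaths without a VL are already outside the population in those tables.

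In the same sentence, reconcile the 22-30 week window with the 22-40 week primary window in SAP 6.1 and Table 1. State whether the analysis is primary (protocol 9.2.1) or supplementary (SAP 4.3).

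If a VL-only result is also shown, label it as suppression among those alive with a measured VL, present deaths by arm beside it, and do not use it as support for non-inferiority.

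The cost is a short text change and one inclusion condition in the code. Deaths and whether they were due to trauma are already recorded (protocol 6.11), and the sample size stays at 295 per arm. The downside is that the set is no longer VL-measured only and its suppression percentages become slightly lower. In the example worked in full, the control percentage falls from 85.2% to 0.75/0.90 = 83.3%.

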### 4.1 Endpoints

#### 4.1.1 Primary endpoint

- HIV viral suppression <400 copies/mL 26 (22 – 40) weeks after enrolment (obtained from routine laboratory reports at study facility, from laboratory reports of referral facility in case of transfer-out, or from dried blood spot (DBS) sample for participants without documented clinic visit but found during home visit tracing)

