## 4.3 Analysis populations

As per the protocol (2), all analyses will be done by the trial statistician using R (the R Foundation for Statistical Computing) or Stata (version 18, Stata Corporation, Austin/Texas, USA). Analysis will follow CONSORT guidelines. Primary analyses for the non-inferiority comparison will be performed on both the ITT and per protocol (PP) sets (3).

Our approaches for the primary outcome are further detailed in the context of the estimands framework in Tables 2a and 2b (4).

For secondary outcomes related to VL (achieving viral suppression defined by other thresholds), we will employ similar methods as for the primary outcome (both superiority and non-inferiority comparisons).

For the remaining secondary outcomes, we will employ similar methods as for the primary outcome but under the superiority comparison only.

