### Primary outcome

The study visit for primary outcome assessment was scheduled together with the routine 6 month ART refill visit. Study staff tried to ensure that a VL was measured for the assessment of the study primary endpoint. If VL was not successfully measured or a study visit did not occur, participants were traced in order to obtain the outcome assessment.

Viral suppression is defined as a HIV VL <400 copies/mL during the defined analysis window of 154-280 days (Table 1). The viral load was obtained from routine laboratory reports at study facilities, from laboratory reports of referral facility in case of transfer out, or from dried blood spot (DBS) sample for participants without documented clinic visit but found during home visit tracing.

If more than one VL is available for a participant during this window, any value meeting the definition of viral suppression will be considered and defined as the participant achieving the primary endpoint.

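### The SAP's complete-case analysis takes viral loads from weeks 22–30 only, although the primary endpoint window is weeks 22–40, and the protocol's no-tracing sensitivity analysis is not carried over

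*SAP*

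**What the plan says.** The endpoint is the same in both documents. Protocol 4.1.1 gives "HIV viral suppression <400 copies/mL 26 (22 – 40) weeks after enrolment". SAP 6.1 (Primary outcome) takes VL below 400 copies/mL "during the defined analysis window of 154-280 days", and SAP Table 1 repeats weeks 22–40. In that table, weeks 22–30 is the window for the study visit.

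The supportive analyses differ:

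- **Complete case, protocol 9.2:** "Complete-case set: all individuals for which the endpoint data could be ascertained".
- **Complete case, SAP 6.2:** "only individuals with a valid VL measurement in the endpoint window of 22 to 30 weeks is included".
- **Role of the complete-case set:** protocol 9.2.1 says "Primary analyses for the non-inferiority comparison will be performed on the mITT, per-protocol, and complete case sets". SAP 4.3 says "Primary analyses for the non-inferiority comparison will be performed on both the ITT and per protocol (PP) sets".
- **Tracing data:** protocol 9.2.1 adds a sensitivity analysis in which "primary endpoint information obtained from the tracing visit will not be included". The SAP contains no such analysis. SAP 6.2 only undertakes to report what share of the primary outcome data came from tracing.

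The SAP gives no reason for either change, and no entry in its revision history names them.

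**The concern.** In the primary analysis, a participant with no VL counts as not suppressed. A complete-case analysis is the natural check on how far the result depends on that rule. It is also the only one firmly planned: in SAP 6.3 and the footnotes to Tables 2a and 2b, imputation is conditional on there being enough cases.

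With a cut-off at week 30, the check changes two things at once. It removes participants with no VL, which is its purpose. It also removes participants who have a valid VL inside the endpoint window and who count in the primary analysis. Tracing in weeks 31–40 exists to obtain those results.

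The narrower window also selects on having a VL sampled by week 30. That is close to retention in care, a secondary endpoint tested for superiority, and protocol 2.3 suggests that same-day ART may improve it. If the arms differ in how many participants are reached only by tracing, the complete-case estimate can move for reasons unrelated to missing data. The protocol's no-tracing analysis would show how much the primary result owes to tracing, but the SAP does not carry it over.

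**Working it through.** **The plan's own figure.** Inputs from protocol 9.1 and the synopsis: 75% suppressed in both arms, margin 10 points, one-sided alpha 0.025, power 80%. n per arm = (1.960 + 0.842)² × 2 × 0.75 × 0.25 / 0.10² = 294.3, rounded up to 295. This matches the stated 295 (590 in total), and nothing below changes it.

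**Windows in days.** Weeks 22–30 = days 154–210. Weeks 22–40 = days 154–280. Tracing in weeks 31–40 = days 217–280. SAP 3.7 dates a laboratory result by when the sample was taken. So every sample taken during tracing falls outside the SAP's complete-case window, as does any routine VL sampled on days 211–280.

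**Level of the estimates (assumed inputs).** The documents do not give the share of participants whose only VL is after week 30. Let t be that share and s the proportion of them suppressed, with 75% suppressed overall and 10% with no VL. I take t = 5–15% and s = 40–75%.

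- Complete case, weeks 22–40: 0.75/0.90 = 83%, about 266 per arm.
- Complete case, weeks 22–30: (0.75 − t·s)/(0.90 − t) = 84% to 92%, about 221 to 251 per arm.
- Tracing VLs removed and counted as failures: 0.75 − t·s = 64% to 73%, 295 per arm.

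**Difference between arms (assumed inputs).** Take 10% with no VL in each arm, 92% suppressed at the visit and 50% among traced participants. Complete case over weeks 22–40 = [(0.90 − t) × 0.92 + t × 0.50]/0.90.

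- t = 5%: 0.807/0.90 = 89.7%. t = 15%: 0.765/0.90 = 85.0%. Difference 4.7 points.
- t = 8%: 0.7944/0.90 = 88.3%. t = 12%: 0.7776/0.90 = 86.4%. Difference 1.9 points.
- Weeks 22–30: 92% in both arms, difference 0.
- Primary rule (no VL = failure) at 5% v 15%: 80.7% v 76.5%, difference 4.2 points.

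The sign depends on which arm needs more tracing.

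**Example with unequal missingness (assumed counts, 295 per arm).**

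| | ART first | TB results first |
|---|---|---|
| Weeks 22–30, suppressed / not | 205 / 20 | 215 / 20 |
| Tracing, suppressed / not | 15 / 25 | 6 / 14 |
| No VL | 30 | 40 |

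- Primary rule: 220/295 − 221/295 = −0.3 points.
- Complete case, weeks 22–40: 220/265 − 221/255 = −3.6 points.
- Complete case, weeks 22–30: 205/225 − 215/235 = −0.4 points.
- Tracing VLs counted as failures: 205/295 − 215/295 = −3.4 points.

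Here the SAP's version agrees with the primary result, while both protocol analyses differ from it by about 3 points.

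**The case against.** The best defence is that weeks 22–30 was a deliberate choice, loosely worded. Protocol 6.12 (footnote 1) and protocol 7.2.3 also describe the period to week 30 as an endpoint window. A reader might infer that weeks 22–40 is used everywhere else; these two places show that it is not. They explain how the wording could arise, but they do not define the outcome. Where the primary outcome is defined, it runs to week 40.

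Further points stand in whole or in part:

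- A reader might infer that every traced participant is lost. That goes too far. Under protocol 6.11, tracing is triggered by having no VL at the study facility, and reports are then sought from referral facilities. A traced transfer-out sampled elsewhere in weeks 22–30 stays in.
- A reader might infer that the SAP merged two protocol analyses into one. The documents show an omission only; the SAP does not present its complete-case analysis as a substitute.
- The protocol does not say how participants with a tracing-only VL are handled once those data are left out. Counting them as not suppressed is the natural reading, but it is not written.
- A 22–40 week complete-case set also conditions on a post-randomisation event, namely attending or being found. The difference is one of degree.
- The 4.7-point figure is no estimate of a true effect. It needs a threefold difference in tracing between arms, and under those inputs the primary analysis itself shows 4.2 points. The count example shows that this need not happen when missingness also differs, but those counts are assumed too.
- The SAP has other information on missingness: outcome completeness by arm, conditional imputation, and the share of outcomes from tracing.

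**Conclusion.** The point holds as an error in a supportive analysis. The SAP's complete-case window stops at day 210, whereas the endpoint window runs to day 280. The analysis therefore discards valid in-window VLs that the primary analysis uses, and it is not the complete-case set of protocol 9.2. Separately, the protocol's sensitivity analysis without tracing data is missing from the SAP.

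The size of the effect is unknown. It is about 2 to 5 points on the complete-case risk difference under the assumed tracing shares of 8% v 12% to 5% v 15%, with 10% missing per arm and suppression of 92% at the visit and 50% among those traced. With equal tracing shares in the two arms and the other inputs unchanged, the shift would be zero.

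A reader might infer that the non-inferiority conclusion is at risk. The documents do not support this. The decision in SAP 3.4 and 6.2, and in the protocol synopsis, rests on the ITT (mITT in the protocol) and per-protocol sets. Those analyses, the endpoint definition and the sample size are untouched.

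**What to change.** In SAP 6.2:

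1. Set the complete-case window to days 154–280. State whether a known non-traumatic death before any VL counts as an ascertained failure or is left out. Protocol 9.2 refers to ascertained endpoint data rather than to a valid VL, so this is open.
2. Restore the no-tracing sensitivity analysis as a separate, named analysis and write down its handling rule. The natural reading of protocol 9.2.1 is the full denominator, with participants who have only a tracing VL counted as not suppressed.
3. If a visit-window analysis over weeks 22–30 is also wanted, keep it as an additional analysis, label it as such, justify it, and do not call that period the endpoint window.

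If either departure from the protocol was intended, the SAP should say so and give the reason. The cost is SAP wording and one extra model run, with no new data.

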#### 9.2.2 Secondary, subgroup and exploratory analysis

The secondary endpoints of ART initiation within 7 or 28 days after enrollment and retention in care will be assessed for superiority. Secondary endpoints will be analyzed with logistic regression models adjusted for stratification factors and results will be presented as risk differences and 95% confidence intervals.

Non-traumatic mortality, hospitalizations, SAEs, AESIs and incidence of TB will be summarized descriptively as events are expected to be rare.

We plan to assess the potential effect modification of key factors (age groups, CD4-count, country) on the primary outcome by including interaction terms in the model. If the interaction term is found to be significant, effect estimates will be summarized descriptively by subgroup. The study is not powered for these pre-planned subgroup analyses so all results will be considered exploratory.

The statistical analysis plan will provide all further details.

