We will conduct a planned subgroup analysis by country. Effect estimates of the primary outcome will be presented descriptively by subgroup. Potential effect modification of the primary outcome by ART status will be assessed by including interaction term between arm and the corresponding variable in the model. If the interaction term is found to be

significant ( $p<0.1$ ), effect estimates will be summarized descriptively by subgroup. The study is not powered for these pre-planned subgroup analyses so all results will be considered exploratory.

Given that VLs were done through the routine health system, in Malawi, some DBS tests were done on platforms with a limit of quantification at 839 copies/mL (Abbott m2000/real time) or 883 copies/mL (Panther Hologic). After conferring with experts, we have concluded to consider these tests as suppressed at the limit of 400 copies/mL for the primary analysis if the PCR target was not detected (as opposed to target detection but not quantifiable). As a sensitivity analysis of the primary outcome, we will consider these as not suppressed.

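### The SAP omits the protocol's exploratory age-group and CD4 effect-modification analyses of viral suppression, adds ART status, and shows ART-status estimates only if the interaction has p<0.1

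*SAP*

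**What the plan says.** **Protocol 9.2.2.** The protocol names three factors, each to be examined with an interaction term: "We plan to assess the potential effect modification of key factors (age groups, CD4-count, country) on the primary outcome". It already makes display depend on the result: "If the interaction term is found to be significant, effect estimates will be summarized descriptively by subgroup". It gives no significance level and no categories for age or CD4 count.

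**SAP 6.2, Primary outcome analysis.** Country stays, with no condition on display: "We will conduct a planned subgroup analysis by country. Effect estimates of the primary outcome will be presented descriptively by subgroup". The only interaction named is with ART status: "Potential effect modification of the primary outcome by ART status will be assessed by including interaction term". Its stratum estimates appear only when the term is "significant ( $p<0.1$ ), effect estimates will be summarized descriptively by subgroup".

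**Age and CD4 count elsewhere in the SAP.** They are among the baseline covariates that may enter the primary model ("age, gender, CD4 cell count, and ART status) if found to be unbalanced between study arms"), and they are rows in the baseline shell table (SAP 8.2). Neither use estimates a treatment effect within a stratum.

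**Explanation and status.** SAP 6.2 gives no reason for the change, and the SAP revision history does not mention it. Both documents describe the subgroup analyses as pre-planned, unpowered and exploratory.

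**The concern.** There are two separate issues.

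The first is consistency. Two of the three factors in the protocol have gone and a new one has come in, with no record of why. A reader comparing the SAP with the protocol cannot tell which subgroup analyses were fixed at the design stage. The omitted factors are not incidental. Protocol 2.2 says IRIS risk is higher at lower baseline CD4 counts and with earlier ART, so CD4 count is a natural place to ask whether the strategy effect differs. Protocol 3.2 includes adolescents so that ART-timing policy for them need not be extrapolated from adults.

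The second is the display rule. When an underpowered test decides whether stratum estimates are printed, real differences are usually not shown, and those that are shown tend to be too large. The SAP applies this rule to ART status but not to country, within the same paragraph.

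What is at stake is the completeness and fair reading of exploratory results on viral suppression.

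**Working it through.** **1. The two factor lists**

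| Factor | Protocol 9.2.2 | SAP 6.2 |
|---|---|---|
| Country | Interaction; estimates if significant | Estimates always shown |
| Age group | Interaction; estimates if significant | Absent |
| CD4 count | Interaction; estimates if significant | Absent |
| ART status | Absent | Interaction; estimates if p<0.1 |

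**2. Inputs for the illustration**

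Protocol 9.1 and SAP 3.3 give 295 per arm, 75% suppression, a 10-point margin, 80% power and one-sided alpha 0.025. The variance of a single binary outcome is 0.75 × 0.25 = 0.1875. The documents do not give the share *s* of participants in the smaller stratum, so a range is assumed.

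**3. The plan's own figure**

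n per arm = 2 × 0.1875 × (1.960 + 0.842)² / 0.10² = 294.3, rounded up to 295. At 295 per arm the power is 80.1%. The stated sample size reproduces; there is no numerical error in the plan here.

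**4. Chance that estimates are displayed**

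Let D be the difference between the two stratum risk differences. With 75% suppression used throughout for the variance:

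SE(D) = √[(2 × 0.1875 / 295) × (1/s + 1/(1 − s))]

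P(display) = 1 − Φ(1.645 − D/SE) + Φ(−1.645 − D/SE)

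| s | SE(D) | D = 0 | D = 10 points | D = 20 points |
|---|---|---|---|---|
| 0.5 | 0.0713 | 10% | 40.5% | 87.7% |
| 0.3 | 0.0778 | 10% | 36.1% | 82.3% |
| 0.2 | 0.0891 | 10% | 30.3% | 72.5% |
| 0.1 | 0.1188 | 10% | 21.7% | 51.6% |

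A true difference as large as the whole non-inferiority margin is therefore displayed about 22-41% of the time.

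**5. Selection among displayed estimates**

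To pass p<0.1, the observed D must exceed 1.645 × SE(D) in absolute value. That is 11.7 points (s = 0.5), 12.8 (s = 0.3), 14.7 (s = 0.2) or 19.5 (s = 0.1). If the true value is 10 points, every displayed estimate is either larger than the truth or of the wrong sign.

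**6. Precision if estimates are always shown**

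The 95% CI half-width for the risk difference in the smaller stratum is 1.96 × √[2 × 0.1875 / (295s)]. This gives 9.9 points (s = 0.5), 12.8 (0.3), 15.6 (0.2), 22.1 (0.1) and 31.3 (0.05).

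**7. Scale**

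Steps 4 to 6 use the risk-difference scale, the summary measure in SAP Tables 2a and 2b. SAP 6.2 fits a log-link model, so its interaction term would ordinarily be tested on the ratio scale. The SAP does not say which scale is meant, and the figures could differ on the ratio scale.

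**The case against.** Much of the case on the other side stands.

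- **The display rule comes from the protocol.** A reader might infer that the SAP introduced result-dependent display. It did not. It stated a level, and it removed the condition for country. If the protocol's unspecified significance meant 0.05 (an assumption), the chance of showing a true 10-point difference would be 28.9%, 25.1%, 20.2% and 13.4% for s = 0.5, 0.3, 0.2 and 0.1. The SAP's 0.1 is the looser rule.
- **These are not safety analyses.** A reader might infer that safety subgroups have been lost. The omitted analyses concern viral suppression. AESIs, which capture TB-IRIS, are descriptive only in both documents, and neither plans them by CD4 count. For adolescents, Protocol 11.6 reports no indication that either strategy leads to worse outcomes.
- **ART status is a sensible factor.** Protocol 9.2.1 already lists naive versus reinitiating among the important baseline characteristics, and Protocol 9.2.2 leaves further detail to the SAP. That supports adding a factor; it does not explain removing two.
- **Related material remains.** The SAP keeps an exploratory objective on risk factors for adverse outcomes (2.2) and a description of participants hospitalised or deceased (6.1). Neither estimates effect modification of the primary outcome.
- **The arithmetic is limited.** It applies to the ART-status condition only and says nothing about the cost of omitting age or CD4 count. The interaction is assessed whether or not stratum estimates are printed, so a difference is not wholly concealed.
- **Restored strata may be uninformative.** If adolescents were 5-10% of participants (an assumption), the half-width would be 22-31 points.

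**Conclusion.** The point holds as an unexplained difference between protocol and SAP in the exploratory subgroup factors, together with a result-dependent display rule for ART status that the SAP carries over from the protocol. Under the assumed stratum shares of 10-50%, with 295 per arm, 75% suppression and the risk-difference scale, a margin-sized 10-point difference would be displayed about 22-41% of the time, and what is displayed is selected for apparent heterogeneity.

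The primary estimand, margin, test and non-inferiority conclusion are unaffected, and the analyses would not answer whether safety events differ by subgroup.

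A reader might also infer from the dates that outcome data drove the change. The trial is open-label, the first SAP draft is dated 30 May 2024 and version 2.0 is dated 14 January 2025, after the planned last participant out in December 2024. Nothing in the documents shows that results influenced the choice. The dates are only a reason to record the rationale. Nor can it be checked whether the published protocol that the SAP cites lists other factors; the comparison here is with protocol version 1.3.

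**What to change.** In SAP 6.2:

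1. Restore age group and CD4 count alongside country, with categories fixed before outcomes are compared by arm. The documents already use 12-17 versus 18 years and older, and a CD4 level of 200 for CrAg testing, so these are available candidates.
2. Label ART status as a factor added in the SAP, and enter the change with its reason in the revision history.
3. For every level of all four factors, report arm-specific suppression rates, the risk difference with 95% CI, and the interaction p-value, with no significance condition on display.
4. State the scale on which the interaction is tested.

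The cost is SAP wording and two more exploratory models on variables already collected. Intervals will be wide in small strata such as adolescents. Four interaction p-values also make a chance finding more likely: with no true heterogeneity and independent tests, the chance of at least one below 0.1 is 1 − 0.9⁴ = 34%. The text should therefore present them as descriptive and keep the existing statement that these analyses are exploratory and unpowered.
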